7.3. Vital Signs

Vital signs (systolic and diastolic blood pressure [mmHg], pulse [beats/min]) at each visit, and change from baseline at each visit will be summarized for the Safety Analysis Set using descriptive statistics (n, mean, SD, median, Q1, Q3, minimum, and maximum) by treatment group. The baseline value will be defined as the last available value collected on or prior to the date/time of first dose of study drug. Change from baseline to a postbaseline visit will be defined as the postbaseline value minus the baseline value.

In the case of multiple values in an analysis window, data will be selected for analysis as described in Section 3.7.3 (Selection of Data in the Event of Multiple Records in a Window). No inferential statistics will be generated.

A by-subject listing of vital signs (systolic and diastolic blood pressure [mmHg], pulse [beats/min], respiration [breaths/min], and body temperature [$^{\circ}$ C]) will be provided by subject ID number and visit in chronological order.

7.4. Body Weight, Height and BMI

An age- and sex-specific percentile will be derived for each weight, height and BMI measurement according to the downloadable SAS program available on the Centers for Disease Control (CDC) website using the year 2000 growth charts. Methods and SAS program published on the following CDC website will be applied to calculate the percentile {Centers for Disease Control and Prevention (CDC) 2016a, Centers for Disease Control and Prevention (CDC) 2016b}.

Body weight, height, BMI and percentiles for body weight, height, BMI at each visit, and change from baseline at each visit will be summarized for the Safety Analysis Set using descriptive statistics (n, mean, SD, median, Q1, Q3, minimum, and maximum) by treatment group.

In the case of multiple values in an analysis window, data will be selected for analysis as described in Section 3.7.3 (Selection of Data in the Event of Multiple Records in a Window). No inferential statistics will be generated.

A by-subject listing of body weight, weight percentile, height, height percentile, BMI and BMI percentile will be provided by subject ID number and visit in chronological order.

7.5. Mid-Parental Height Assessment

The calculation of mid-parental height has been a standard procedure for assessing individual child's future adult height since it was first described by Tanner {Tanner 1970}. Mid-parental height was calculated as the average of father's and mother's height. For boys, calculate the sex-adjusted mid-parental height by adding 2.5 inch or 6.5 cm from the mean of the parents' heights. For girls, subtract 2.5 inch or 6.5 cm from the mean of the parents' heights. If any one of parents' heights is missing, the calculation will be excluded.

A by-subject listing of parents' heights and derived mid-parental height will be provided by subject ID number in ascending order.

7.6. Bone Age Assessment

A single X-ray of the left wrist, hand, and fingers will be performed at Day 1 Visit and post-treatment Week 24. Local radiologist will determine the bone age from x-ray.

Bone age at baseline visit, FU-24 visit and change from baseline visit will be summarized for the Safety Analysis Set using descriptive statistics (n, mean, SD, median, Q1, Q3, minimum, and maximum) by treatment group.

A by-subject listing of bone age will be provided by subject ID number in ascending order and visit in chronological order.

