1.1. Study Objectives

The primary objectives of this study are as follows:

- The primary objective of the pharmacokinetics (PK) Lead-in Phase of this study is to evaluate the steady state PK and confirm the dose of Ledipasvir/Sofosbuvir Fixed Dose Combination (LDV/SOF FDC) in hepatitis C virus (HCV)-infected pediatric subjects.
- The primary objective of the Treatment Phase of this study is to evaluate the safety and tolerability of LDV/SOF FDC ± ribavirin (RBV) for 12 or 24 weeks in HCV-infected pediatric subjects.

The secondary objectives of this study are as follows:

- The secondary objective of the PK Lead-in Phase of this study is to evaluate the safety and tolerability of 10 days of dosing of LDV/SOF FDC in HCV-infected pediatric subjects.
- The secondary objectives of the Treatment Phase of this study are:
 - To determine the antiviral efficacy of 12 or 24 weeks of LDV/SOF FDC ± RBV treatment in chronic HCV-infected subjects (including the impact of HCV genotype, IL28B genotype, and prior treatment experience), as assessed by the proportion of subjects with sustained viral response 12 weeks after discontinuation of therapy (SVR12)
 - To determine the antiviral efficacy of 12 or 24 weeks of LDV/SOF FDC ± RBV treatment in chronic HCV-infected subjects, as assessed by the proportion of subjects with sustained viral response 4 and 24 weeks after discontinuation of therapy (SVR4 and SVR24)
 - To evaluate the kinetics of circulating HCV RNA during treatment and after completion of treatment
 - To evaluate the emergence of viral resistance to LDV and SOF during treatment and after completion of treatment
 - To evaluate the acceptability assessed by swallowability of tablets and palatability of granules
 - To evaluate the effect of growth and development on pediatric subjects during and after treatment

The exploratory objective of this study is as follows:

- PPD [Redacted]

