1.2.3. Study Duration

The total time to complete all study visits is up to approximately 40 weeks for subjects treated with 12 weeks of therapy and 52 weeks for subjects treated for 24 weeks of therapy including the following periods:

- 28-day (4-week) screening period
- 12 or 24 week treatment period
- 24-week posttreatment period

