3.2. Subject Grouping

For analyses based on the All Enrolled Analysis Set or FAS, subjects will be grouped according to the treatment to which they were enrolled. For analyses based on the Safety Analysis Set, subjects will be grouped according to the actual treatment received. The actual treatment received is defined as the enrolled treatment except for subjects who received treatment that differs from the enrolled treatment for the entire treatment duration. In this case, the actual treatment received is defined as the treatment received for the entire treatment duration.

Generally, subjects are analyzed, except for the safety analysis, by treatment groups based on age group, HCV genotype, prior treatment experience, cirrhosis status, and treatment duration:

Table 3-1. Non-safety Treatment Groups*

12 to < 18 Years Old		3 to < 12 Years Old			
LDV/SOF (90/400 mg) 12 Weeks		LDV/SOF (45/200 mg or 33.75/150 mg) 12 Weeks		LDV/SOF (45/200 mg) 24 Weeks	LDV/SOF+RBV (45/200 mg) 24 Weeks
GT1 TN w/ or w/o cirrhosis (N =)	GT1 TE without cirrhosis (N =)	GT1, GT4 TN w/ or w/o cirrhosis (N =)	GT1 TE without cirrhosis (N =)	GT1 TE with cirrhosis (N =)	GT3 TE w/ or w/o cirrhosis (N =)
6 to < 12 Years Old			3 to < 6 Years Old		
LDV/SOF (45/200 mg) 12 Weeks		LDV/SOF (45/200 mg) 24 Weeks	LDV/SOF+RBV (45/200 mg) 24Weeks	LDV/SOF (45/200 mg or 33.75/150 mg) 12 Weeks	
GT1, GT4 TN w/ or w/o cirrhosis (N =)	GT1 TE without cirrhosis (N =)	GT1 TE with cirrhosis (N =)	GT3 TE w/ or w/o cirrhosis (N =)	GT1, GT4 TN w/ or w/o cirrhosis (N =)	

GT = genotype, TN = Treatment Naïve, TE = Treatment Experienced, w/ = with, w/o = without
 *Treatment Groups reflect the subjects actually enrolled.

For the safety analysis, subjects will be analyzed by the following groups based on age group, treatment regimen and duration:

Table 3-2. Safety Treatment Groups

12 to < 18 Years Old	3 to < 12 Years Old		
LDV/SOF (90/400 mg) 12 Weeks (N =)	LDV/SOF (45/200 mg or 33.75/150 mg) 12 Weeks (N =)	LDV/SOF (45/200 mg) 24 Weeks (N =)	LDV/SOF+RBV (45/200 mg) 24 Weeks (N =)
6 to < 12 Years Old			3 to < 6 Years Old
LDV/SOF (45/200 mg) 12 Weeks (N =)	LDV/SOF (45/200 mg) 24 Weeks (N =)	LDV/SOF+RBV (45/200 mg) 24 Weeks (N =)	LDV/SOF (45/200 mg or 33.75/150 mg) 12 Weeks (N =)

Subjects in the 3 to < 6 years of age group will have additional selected efficacy and safety analyses performed according to baseline weight in the following subgroups:

Table 3-3. Subgroups for Selected Analyses in 3 to < 6 years of Age

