4.2.2. Adherence to Study Drug

The level of adherence to individual study drug will be assessed separately based on the total amount of individual study drug administered relative to the total amount of individual study drug prescribed. In this study, LDV/SOF FDC 90/400 mg tablets, LDV/SOF FDC 22.5/100 mg tablets, and LDV/SOF 11.25/50 mg packets containing granules have been used. For RBV, both REBETOL capsules and REBETOL RBV oral solution could be used. Each capsule contains 200 mg RBV and the oral solution contains 40 mg RBV per mL.

Given the fact that multiple formulations of the study drug have been used in this study, the adherence will be calculated based on the amount of LDV/SOF FDC (mg) or RBV (mg) by the following formula:

$$\text{Level of Adherence(\%)} = \left(\frac{\text{Total Amount of Study Drug Administered}}{\text{Total Amount of Study Drug Prescribed at baseline}} \right) \times 100$$

Where the presumed total amount of study drug (mg) administered to a subject will be determined by the data collected on the drug accountability eCRF using the following formula:

$$\text{Total Amount of Study Drug (mg) Administered} = (\sum \text{Total Amount of Study Drug (mg) Dispensed}) - (\sum \text{Total Amount of Study Drug (mg) Returned})$$

Note: If calculated adherence is greater than 100%, the result will be set to 100%.

The total amount of prescribed LDV/SOF FDC (mg) for 12 weeks and 24 weeks are as follows:

Age Group and Body Weight	LDV/SOF Daily Dose	Total Amount of LDV/SOF Prescribed for 12 Weeks	Total Amount of LDV/SOF Prescribed for 24 Weeks
12 to <18 years any weight	490 mg/day	41160 mg	N/A*
6 to <12 years any weight	245 mg/day	20580 mg	41160 mg
3 to <6 years weighing ≥17 kg	245 mg/day	20580 mg	N/A*
3 to <6 years weighing <17 kg	183.75 mg/day	15435 mg	N/A*

*Note: No subject 12 to <18 or 3 to <6 years old was assigned to 24 weeks of treatment.

For subjects infected with HCV GT3, RBV was prescribed by weight at baseline. The total amount of RBV (mg) prescribed for 24 weeks is as follows:

Body Weight kg (lbs.)	RBV Daily Dose	RBV Number of Capsules	Total Amount of RBV Prescribed for 24 Weeks
<47 (<103)	15 mg/kg/day	Use Oral Solution. Divided dose in the morning and evening.	2,520 mg/kg
47-49 (103-108)	600 mg/day	1 × 200-mg capsules A.M. 2 × 200-mg capsules P.M.	504 capsules (100800 mg)
50-65 (110 – 143)	800 mg/day	2 × 200-mg capsules A.M. 2 × 200-mg capsules P.M.	672 capsules (134400 mg)

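### SAP 7.6 summarises bone age only as raw values and raw change, so its tables do not separate normal ageing from delayed or advanced skeletal maturation

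*SAP*

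**What the plan says.** SAP 7.6 states the timing: "A single X-ray of the left wrist, hand, and fingers will be performed at Day 1 Visit and post-treatment Week 24". A local radiologist reads the films. The analysis is one sentence: "Bone age at baseline visit, FU-24 visit and change from baseline visit will be summarized", with descriptive statistics by treatment group on the Safety Analysis Set, plus a by-subject listing. SAP 5.2 also lists baseline bone age in years among the baseline characteristics.

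Neither document plans a difference from chronological age, a ratio, a z-score or an expected change. Protocol 6.6.6 covers collection only, and protocol 9.5.4 has no bone age analysis, so SAP 7.6 and the baseline row in SAP 5.2 are the whole plan for this measure.

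The objective it serves is secondary: "To evaluate the effect of growth and development on pediatric subjects during and after treatment" (SAP 1.1). By contrast, SAP 7.4 converts weight, height and BMI to percentiles specific to age and sex.

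For safety tables, SAP 3.2 says that "subjects will be analyzed by the following groups based on age group, treatment regimen and duration". SAP 4.2.2 notes: "No subject 12 to <18 or 3 to <6 years old was assigned to 24 weeks of treatment".

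**The concern.** A raw rise in bone age mostly measures how long the child was followed. The trial has no control arm, so nothing in the table shows what rise normal maturation would have produced. Chronological age is the one reference available for every child, and the planned summary does not use it.

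What is at stake is how one descriptive safety table reads. A positive mean change looks reassuring even if maturation has slowed, because slowed maturation still gives a positive change. The built-in ageing is also larger for the 24-week regimens, which include the ribavirin group, and protocol 1.1 itself reports concern about ribavirin (with peginterferon) and growth. The SAP already applies an age reference to the other growth measures, so bone age is the exception.

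**Working it through.** **The plan's own figure.** SAP 1.2.3 gives a 4-week screening period, a "12 or 24 week treatment period" and a "24-week posttreatment period", for a total of "approximately 40 weeks for subjects treated with 12 weeks of therapy and 52 weeks for subjects treated for 24 weeks of therapy".
- 12-week regimen: 4 + 12 + 24 = 40 weeks.
- 24-week regimen: 4 + 24 + 24 = 52 weeks.

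Both totals reproduce exactly.

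**Interval between the two X-rays.** This is the total minus screening, for a completer on schedule.
- 12-week regimen: 40 − 4 = 36 weeks; 36 × 7 / 365.25 = 0.69 years.
- 24-week regimen: 52 − 4 = 48 weeks; 48 × 7 / 365.25 = 0.92 years.
- Difference: 12 × 7 / 365.25 = 0.23 years, or about 2.8 months.

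Counting days from first dose (7 × treatment weeks − 1 + 168) gives 251 and 335 days, which round to the same values.

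**Expected table entry with no drug effect.** Assume bone age advances on average one year per calendar year. The planned change is then about +0.69 or +0.92 years. Bone age minus chronological age has an expected change of 0 under both regimens.

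**How a departure would look.** The documents give no effect size, so these are assumptions.
- A delay of 0.2 years on 12 weeks: 0.69 − 0.20 = +0.49 years. For delays of 0.1 to 0.3 years the entry is +0.59 to +0.39 years. All are gains on the face of the table.
- Maturation at 75% of the normal rate on 24 weeks: 0.92 × 0.75 = 0.69 years, equal to normal maturation on 12 weeks. At 50% it is 0.46 years.

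**Departures from the nominal interval.**
- Subjects who stop early still enter post-treatment follow-up (protocol 3.5), timed from discontinuation (protocol 3.2.2). Stopping at Week 4 gives (28 − 1 + 168) / 365.25 = 0.53 years.
- SAP Table 3-5 does not name bone age. If its FU-24 window for weight and height (days 147 to 210) were applied, which is an assumption, the interval runs from 230 to 293 days (0.63 to 0.80 years) on 12 weeks and from 314 to 377 days (0.86 to 1.03 years) on 24 weeks.

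**What the planned tables can and cannot yield.** Mean age (SAP 5.1) and mean bone age (SAP 5.2) at baseline are both tabulated, so the mean gap at baseline can be read off, missing data aside. Its spread cannot: Var(bone age − age) = Var(bone age) + Var(age) − 2 Cov(bone age, age), and no table gives the covariance. Quartiles and extremes of the difference are likewise not recoverable from the separate summaries. No chronological age at FU-24 is summarised.

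**The case against.** The strongest reply is that the separation is easy. Safety columns never mix durations, and the nominal interval is fixed within a column, so one subtraction recovers the mean departure from normal ageing. Individual gaps can be worked out from the bone age and demographic listings. For completers on schedule, the change in bone age minus chronological age is just the raw change less a constant, so its spread is already shown. All of this stands. A reader might infer that the plan makes ageing and maturation impossible to separate; the documents do not support that.

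A reader might also infer that the 0.23-year gap will create a false difference between regimens. The documents do not support this either. No comparison between regimens is planned. The 24-week columns arise only at 6 to <12 years (and in the pooled 3 to <12 display), and they already differ from the 12-week columns in genotype, prior treatment, cirrhosis status or ribavirin use.

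Two further points stand in part. The growth objective does not rest on bone age alone: protocol 9.1.3 gives height, weight and Tanner stage as its examples, and the SAP percentiles are age-referenced. And chronological age is not exact for everyone. SAP 3.6 says that some countries collect only birth year, with 01 January then used unless age is captured on the eCRF. That can overstate age by almost a year and make the level look like delay, by more than the illustrative 0.2 years.

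What the reply does not meet is the missing spread and extremes of the individual difference, and the subjects for whom the column constant is wrong.

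**Conclusion.** The point holds as an omitted derivation. The planned bone age summaries contain about 0.69 years (12-week) or 0.92 years (24-week) of expected ageing and do not take it out. Mean departures can be recovered approximately by hand. The distribution of individual bone age minus chronological age cannot be recovered from the tables, and early stoppers and off-schedule X-rays are not corrected.

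This rests on average maturation of one year per calendar year and, for the two figures, on completion and attendance on schedule. The 0.2-year delay and the 75% rate are illustrations only. The documents give no precision for local bone age readings, so they do not show whether a shift of that size would be detectable even after the change. No sample size, error rate or decision rule depends on this table. It is worth changing because the measure serves a stated secondary objective in a trial without a control arm, and the better summary costs almost nothing.

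**What to change.** In SAP 7.6:
- Derive bone age minus chronological age on the date of each X-ray, at Day 1 and FU-24.
- Summarise both levels and the change by the existing safety treatment groups. The change equals the change in bone age minus the time elapsed between the two X-rays.
- Make the change the main summary. It needs only the two X-ray dates, because any error in the birth date cancels.
- Flag subjects whose birth day and month are imputed as 01 January, or exclude them from the level summaries.
- State which X-rays count as FU-24, since Table 3-5 does not cover bone age.
- Keep raw bone age in the listing.
- Label any illustrative delay, such as 0.2 years, as an assumption.

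The cost is SAP wording and one derivation from data already collected, provided the X-ray or visit dates are in the database. The one small drawback is that levels remain approximate for subjects with imputed birth dates.

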7.7. Tanner Pubertal Stage Assessment

The Tanner stages will be used to evaluate the onset and progression of pubertal changes. Females will be rated for pubic hair growth and breast development, and males will be rated for pubic hair growth and genitalia development. If the subject is at a Tanner 5 at Day 1, no further Tanner Pubertal Stage Assessments are to be completed. The Tanner stages (Pubic Hair and Breasts for female; Pubic Hair and Genitalia for male) at EOT, FU-12 and FU-24 visit will be summarized by baseline Tanner stages using frequency count and percentage by sex overall and by sex within each treatment group.

7.8. Prior and Concomitant Medications

Medications collected at screening and during the study will be coded using the current version of the World Health Organization (WHO) Drug dictionary. The medications will be categorized as prior or concomitant using the following definitions:

- Prior medications: any medications taken and stopped prior to or on the date of first study drug administration
- Concomitant medications: any medications taken after the date of first study drug administration and up to the last dosing date of study drug

Concomitant medications will be summarized by preferred name using the number and percentage of subjects for each treatment group. A subject reporting the same medication more than once will be counted only once when calculating the number and percentage of subjects who received that medication. The summary of concomitant medications will be ordered by preferred term in descending frequency. For drugs with the same frequency, sorting will be done alphabetically.

Summaries will be based on the Safety Analysis Set. No inferential statistics will be generated.

For purposes of analysis, any medication with a stop date that is on or prior to the initial study drug dosing date or a start date that is after the last study drug dosing date will be excluded from a concomitant medication summary. If a partial stop date is entered, any medication with the month and year (if day is missing) or year (if day and month are missing) prior to the initial study drug dosing date will be excluded from the concomitant medication summary. If a partial start date is entered, then any medication with the month and year (if day is missing) or year (if day and month are missing) after the study drug stop date will be excluded from the concomitant medication summary. Medications with completely missing dates will be included in the concomitant medication summary.

A summary of prior medications will not be provided.

All prior and concomitant medications (other than per-protocol study drugs) will be provided in a by-subject listing sorted by subject ID number and administration date in chronological order.

7.9. Other Safety Measures

A data listing will be provided for subjects who become pregnant during the study.

7.10. Changes From Protocol-Specified Safety Analyses

There are no deviations from the protocol-specified safety analyses.

8. PHARMACOKINETIC ANALYSES

8.1. PK Analysis in the PK Lead-in Phase (Intensive PK Analysis)

Intensive PK Analysis will be performed using the PK Lead-in Phase Intensive PK Analysis Set. Concentrations of SOF, GS-331007 and LDV from subjects in the PK lead-in Phase over sampling time will be listed and summarized using descriptive statistics (n, arithmetic mean, geometric mean and its 95% confidence interval, coefficient of variation [%CV], SD, median, Q1, Q3, minimum, and maximum) by nominal time and cohort. For Cohorts 1 and 2, plasma samples will be collected for PK analyses following dosing of study drugs on Day 10 at the following time points: 0 (predose), 0.5, 1, 2, 3, 4, 5, 8, and 12 hours postdose. For Cohort 3, plasma samples for PK analyses will be collected at the following time points: 0 (predose), 0.5, 2, 4, 8, and 12 hours postdose. PK parameters from subjects in the PK lead-in Phase will be summarized (e.g; AUC_{τ} , AUC_{last} , C_{max} , T_{max} , C_{last} , T_{last} , C_{τ} , $T_{1/2}$, volume of distribution and clearance, as appropriate) by cohort.

To confirm the appropriateness of LDV/SOF FDC dose for each age group, PK parameters for SOF, GS-331007 and LDV will be compared between each age group from this study and the LDV/SOF FDC NDA patient population (which includes population-PK derived PK exposure data from adult Phase 2 and 3 studies) by carrying out an analysis of variance (ANOVA) for log-transformed AUC_{τ} of GS-331007 and LDV as the primary endpoint and C_{max} of GS-331007 and LDV as a secondary endpoint. Geometric Mean Ratio and its 90% confidence interval will be provided.

